#### **5.4.3. Supportive Analysis of Primary Efficacy Endpoint**

The statistical methods with LOCF for the main analysis will be repeated using the PP population.

A one-sided Mood's median test will be used to compare the treatment groups for the primary endpoint of change from baseline in AN count with LOCF. This test will be conducted at each

analysis visit separately. Only the one-sided p-values and associated medians for each group will be presented for this non-parametric test (no confidence intervals).

For each of the subsets defined in [Section 3.3.2](#), the primary efficacy MMRM analysis will be performed. If there are not enough patients in a subset to perform the MMRM, then descriptive statistics only will be presented for that subset.

#### **5.4.4. Secondary Efficacy Endpoints**

The secondary efficacy endpoints include:

- Percentage of patients achieving HiSCR50 at each analysis visit.
- Percentage of patients achieving [REDACTED] at each analysis visit.
- Percentage of patients achieving NRS30 at Week 12 among patients with Baseline PGA-SP  $\geq 3$ .
- Percentage of patients meeting [REDACTED] criteria at Week 12.
- Change from baseline in IHS-4 at scheduled timepoints in 12-week treatment period
- Change from baseline in Hidradenitis Suppurativa-Physician Global Assessment (HS-PGA) at scheduled timepoints during the 12-week treatment period
- Change from baseline in DLQI at scheduled timepoints for the 12-week treatment period

The HiSCR50, [REDACTED], NRS30, [REDACTED], IHS-4, and DLQI will all be derived per the algorithms indicated in [Section 3.3.8](#), as part of the statistical analysis. All analyses will be based on the analysis visit windows defined in [Section 3.3.9](#). Endpoints will only be presented for those analysis visit windows at which the endpoint was scheduled for collection.

#### **5.4.5. Secondary Efficacy Analysis**

##### MMRM Analyses

For continuous efficacy measures IHS-4, HS-PGA, and DLQI, the descriptive statistics for the calculated scores and the change from baseline in the scores will be reported for each analysis visit at which the assessment was planned for collection.

The change from baseline in the IHS-4, the change from baseline in DLQI, and change from baseline in HS-PGA will be analyzed for inferential results using the methods planned for the primary efficacy analysis with LOCF.

##### Logistic Analyses

For each treatment group, the observed achiever/responder rate for HiSCR50, [REDACTED], NRS30 and [REDACTED] will be reported along with the 90% CI for the response rate using the normal approximation. The difference in observed response rates will also be presented.

---

The percentage of patients achieving HiSCR50, [REDACTED], NRS30, and [REDACTED] at Week 12 and each scheduled analysis visit will be assessed using a Firth's penalized likelihood logistic regression model with fixed effect for treatment and an applicable baseline as a covariate. For HiSCR50, [REDACTED], and [REDACTED], the baseline covariate will be the count of inflammatory abscesses and nodules. For NRS30, the covariate will be the baseline PGA-SP. The analysis on the FAS population will use LOCF for missing values. An additional sensitivity analysis will be conducted for all of these responder endpoints except [REDACTED] where missing will be imputed as non-response.

Inferential results will include model-based responder estimates and associated 90% CIs, differences in estimates and associated 90% CIs for the active group versus placebo, and p-values testing for significance in the difference.

All efficacy data will be presented in data listings.

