## 3. **GENERAL STATISTICAL CONSIDERATIONS**

### **3.1. SAMPLE SIZE AND POWER**

Approximately 90 patients will be randomized (approximately 45 per treatment group) to provide 90.3% power to demonstrate the superiority of ATI-450 to placebo in the reduction in inflammatory nodules and abscesses at Week 12. This power computation assumes that the reduction in the placebo arm will be on average 2.5 nodules/abscesses and the ATI-450 reduction will be on average 4.75 nodules/abscesses. A standard deviation of 3.6 was assumed for the number of nodules/abscesses. These sample size assumptions were based on the values observed in the adalimumab PIONEER I and PIONEER II Phase 3 trials (Frew et al, 2020, see Protocol Section 10.0).

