### **3.2. RANDOMIZATION AND MASKING**

Patients will be randomized to study treatment in a 1:1 ratio to ATI-450 50 mg BID or placebo. All patients will be centrally assigned to randomized study treatment using an Interactive Voice/Web Response System (IxRS). Before the study is initiated, access instructions and directions for the IxRS will be provided to each study center.

This is a double-blind study with limited access to the randomization code. The ATI-450 and placebo tablets will be identical in physical appearance. The treatment each patient will receive will not be disclosed to the Investigator, study center staff, patient, or Sponsor. The treatment codes will be available to a limited number of third-party vendor personnel (IxRS administrative personnel, Clinical Supplies Management personnel, and unblinded Biostatistician) and Data Safety Monitoring Board (DSMB) members, as necessary, for them to support their functions on the study.

The IxRS will be programmed with blind-breaking instructions. In case of an emergency, the

---

Investigator has the sole responsibility for determining if unblinding of a patient's treatment assignment is warranted. Patient safety must always be the first consideration in making such a determination. If the Investigator decides that unblinding is warranted, the Investigator should make every effort to contact the study Medical Monitor prior to unblinding a patient's treatment assignment unless this could delay emergency treatment of the patient. If a patient's treatment assignment is unblinded, the study Medical Monitor must be notified within 24 hours after breaking the blind. The date and reason that the blind was broken must be recorded in the source documentation and eCRF, as applicable.

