#### **3.3.4. Missing Data and Outliers**

Analysis visit windows will be applied as indicated in [Section 3.3.7](#). If an efficacy assessment is not available in an analysis visit window, then last observation carried forward (LOCF) will be applied to obtain a value for that analysis visit window for analyses conducted on the full analysis set population. For categorical efficacy endpoints, an additional sensitivity analysis will be conducted using non-responder imputation for cases where an efficacy assessment is not available in an analysis visit window. Missing data will not be imputed for safety summaries or efficacy summaries on the per protocol population.

There are multiple reasons that an assessment may not be available within an analysis visit windows:

- Clinic visits out of window or missed visits

- Data excluded from use in analysis due to confounding intercurrent event (see [Section 5.4.1.5](#))

For the latter reason, any assessments that occur after a confounding intercurrent event will be considered missing for purpose of analyses.

For analysis visit windows without an assessment, regardless of the reason, the last non-missing value prior to the start of the analysis visit window will replace the missing values. The baseline assessment can be carried forward.

If an AE has missing relationship to the study drug or severity, then that AE will be considered as ‘related’ to the study drug and the severity will be considered as ‘Severe’ in the table summaries, but the AE will be displayed as having a missing relationship or severity in the listings

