#### **5.4.6. Graphical Displays**

For change in inflammatory nodules and abscesses and change in HS-PGA, the LS Mean (90% CI) will be plotted over time. For the binary efficacy endpoints of proportion of patients achieving HiSCR50, NRS30, and [REDACTED] the responder rate (percentage) and 90% CI will be plotted over time by treatment group.

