#### **Section 14.2 Efficacy**

Table 14.2.1.1 Summary of Abscess and Inflammatory Nodule Count Change from Baseline by Analysis Visit FAS Population

Table 14.2.1.2 Summary of Abscess and Inflammatory Nodule Count Change from Baseline by Analysis Visit, PP Population

Table 14.2.1.3 Analysis of Change from Baseline in Abscess and Inflammatory Nodule Count by Analysis Visit FAS Population

Table 14.2.1.4 Analysis of Change from Baseline in Abscess and Inflammatory Nodule Count by Analysis Visit, PP Population

Table 14.2.1.5 Analysis of Median Change from Baseline in Abscess and Inflammatory Nodule Count by Analysis Visit, FAS Population

Table 14.2.1.6.1 Analysis of Change from Baseline in Abscess and Inflammatory Nodule Count by Analysis Visit FAS Population – Baseline Hurley Stage: Mild (I)

Table 14.2.1.6.2 Analysis of Change from Baseline in Abscess and Inflammatory Nodule Count by Analysis Visit FAS Population – Baseline Hurley Stage: Moderate (II)

Table 14.2.1.6.3 Analysis of Change from Baseline in Abscess and Inflammatory Nodule Count by Analysis Visit FAS Population – Baseline Hurley Stage: Severe (III)

Table 14.2.1.6.4 Analysis of Change from Baseline in Abscess and Inflammatory Nodule Count by Analysis Visit FAS Population – Sex: Male

Table 14.2.1.6.5 Analysis of Change from Baseline in Abscess and Inflammatory Nodule Count by Analysis Visit FAS Population – Sex: Female

Table 14.2.1.6.6 Analysis of Change from Baseline in Abscess and Inflammatory Nodule Count by Analysis Visit FAS Population – Baseline BMI: Underweight/normal [ $<25 \text{ kg/m}^2$ ]

Table 14.2.1.6.7 Analysis of Change from Baseline in Abscess and Inflammatory Nodule Count by Analysis Visit FAS Population – Baseline BMI: Overweight [25 to  $<30 \text{ kg/m}^2$ ]

Table 14.2.1.6.8 Analysis of Change from Baseline in Abscess and Inflammatory Nodule Count by Analysis Visit FAS Population – Baseline BMI: and Obese [ $\geq 30 \text{ kg/m}^2$ ]

Table 14.2.2.1 Percentage of Patients Achieving Hidradenitis Suppurativa Clinical Response (HiSCR50) by Analysis Visit FAS Population, Missing Imputed as LOCF

Table 14.2.2.2 Percentage of Patients Achieving Hidradenitis Suppurativa Clinical Response (HiSCR50) by Analysis Visit FAS Population, Missing Imputed as Non-Response

Table 14.2.2.3 Percentage of Patients Achieving Hidradenitis Suppurativa Clinical Response (HiSCR50) by Analysis Visit, PP Population

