## **Figures**

Figure 14.2.1 LS Mean Change from Baseline (90% CI) in Abscess and Inflammatory Nodule Count Over Time by Treatment Group (LOCF), FAS Population

Figure 14.2.2 Responder Rate (90% CI) for HiSCR50 Over Time by Treatment Group (LOCF), FAS Population

Figure 14.2.5 Responder Rate (90% CI) for NRS30 Over Time by Treatment Group (LOCF), FAS Population

Figure 14.2.6 Responder Rate (90% CI) for [REDACTED] Over Time by Treatment Group (LOCF), FAS Population

Figure 14.2.8 LS Mean Change from Baseline (90% CI) in HS-PGA Over Time by Treatment Group, FAS Population

Figure 14.3.4.3.X Mean (+/- SE) Laboratory Parameters Over Time by Treatment Group for CK, Absolute Neutrophils, ALT, AST, and Bilirubin, Safety Population

---

Figure 14.3.5.2 Mean (+/- SE) QTcF Values Over Time by Treatment Group, Safety Population

Figure 14.3.5.3 Mean Plasma Concentration (+/- SD) of ATI-450 Over Time by Treatment Group, PK Population

Figure 14.3.5.4 Mean Plasma Concentration (+/- SD) of CDD-2164 Over Time by Treatment Group, PK Population

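### Normal-approximation 90% CIs for per-arm responder rates fail at low counts with about 45 patients per arm (descriptive output only)

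*SAP*

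**What the plan says.** SAP 5.4.5, under Logistic Analyses, gives two kinds of 90% interval for the responder endpoints.

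- **Observed rate per arm:** reported "along with the 90% CI for the response rate using the normal approximation". The readable text names no exact, score or small-count alternative.
- **Model-based rate per arm:** from a Firth "penalized likelihood logistic regression model with fixed effect for treatment and an applicable baseline as a covariate", fitted at Week 12 and at each scheduled visit. The treatment differences, their 90% CIs and the p-values also come from this model.

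SAP 5.4.6 adds that for the binary endpoints "the responder rate (percentage) and 90% CI will be plotted over time by treatment group". The figure list repeats this, for example "Responder Rate (90% CI) for HiSCR50 Over Time by Treatment Group (LOCF), FAS Population". Neither place says whether the observed-rate or the model-based interval is drawn.

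Three other provisions affect the counts:

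- Section 3.1 sets the size: "Approximately 90 patients will be randomized (approximately 45 per treatment group) to provide 90.3% power".
- NRS30 is assessed only in patients with a baseline skin-pain score of at least 3 (section 3.3.8), so its denominator can be smaller.
- The tables run by analysis visit. The first window covers Days 2 to 11 (Table 2), and under LOCF "The baseline assessment can be carried forward" (section 3.3.4). A carried-forward baseline shows no improvement, so for HiSCR50 and NRS30 it counts as no response.

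**The concern.** The normal-approximation interval takes its width from the observed proportion. As that proportion nears 0 (or 1) the width shrinks to nothing, and the limits stay symmetric about the estimate even when this takes them outside 0 to 100%. With about 45 patients, a visit with few responders would be shown with an interval that is too short or contains impossible values.

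The same section picks Firth regression for these endpoints, a method suited to sparse data that still gives a finite interval at zero responders. One arm at one visit could therefore appear with two 90% intervals that do not overlap. If the figures draw the normal-approximation interval, error bars could vanish or run below zero.

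The stake is how the descriptive results are read. No hypothesis test depends on this interval.

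**Working it through.** **Inputs.** n = 45 per arm (SAP 3.1). Nominal level 90%, so z = 1.645. No expected responder rate is given, so the true rate is varied as an assumption. n = 30 is an assumed NRS30 denominator.

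**Check of the plan's own figure.** The plan states no figure for these intervals, but its power statement confirms the n per arm and the one-sided 0.05 convention that goes with a 90% CI. The difference is 4.75 − 2.5 = 2.25 and the SD is 3.6. The noncentrality is 2.25 / (3.6 × √(2/45)) = 2.965. With 88 degrees of freedom and one-sided 0.05, power is 90.27%, which matches the stated 90.3%. A two-sided 0.05 test would give 83.5%.

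**Intervals at small counts, n = 45.** The normal approximation is p ± 1.645 × √(p(1 − p)/n). For 1 of 45, p = 2.22% and the standard error is √(0.0222 × 0.9778/45) = 2.20%, so the interval is 2.22% ± 3.61%.

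| Responders | Normal approximation | Wilson | Exact (Clopper-Pearson) |
|---|---|---|---|
| 0 | 0.0 to 0.0% | 0 to 5.7% | 0 to 6.4% |
| 1 | −1.4 to 5.8% | 0.5 to 9.4% | 0.1 to 10.1% |
| 2 | −0.6 to 9.5% | 1.5 to 12.6% | 0.8 to 13.3% |
| 18 | 28.0 to 52.0% | 28.9 to 52.2% | 27.7 to 53.3% |

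By symmetry the same failures occur near 45 of 45.

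**Exact coverage.** For each true rate, add the binomial probabilities of the counts whose interval contains it. At a true rate of 2%, the count 0 has probability 0.98^45 = 40% and its zero-width interval misses. That alone takes coverage down to about 60%. At 6%, the counts 0 and 1 both miss, because the upper limit at 1 of 45 is 5.8%.

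| True rate | Normal approximation, n = 45 | Chance of 0 of 45 |
|---|---|---|
| 2% | 60% | 40% |
| 3% | 74% | 25% |
| 5% | 89% | 10% |
| 6% | 74% | 6% |
| 8% | 86% | 2% |
| 10% | 81% | 0.9% |

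Coverage oscillates because counts are discrete, so averages over a range are the fairer summary:

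| n, true rates | Normal approximation, mean (range) | Wilson, mean (range) |
|---|---|---|
| 45, 2 to 10% | 82% (60 to 92%) | 91.5% (87 to 97%) |
| 45, 15 to 50% | 88.6% (84 to 92%) | 90.0% (87 to 93%) |
| 30, 2 to 10% | 76% (45 to 92%) | 92% (83 to 97%) |

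The exact interval averages 96% at n = 45 over 2 to 10%.

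**The model-based interval for the same arm.** With treatment as the only term, Firth's method estimates a 0 of 45 arm as (0 + 0.5)/(45 + 1) = 1.09%. The logit is ln(0.5/45.5) = −4.511, with standard error 1/√(45 × 0.0109 × 0.9891) = 1.438. The Wald limits −4.511 ± 1.645 × 1.438 back-transform to 0.1% and 10.5%. This leaves out the baseline covariate for simplicity, and the SAP does not say how its Firth interval is formed. Adding a simulated baseline count unrelated to response gives a median of 1.1% (0.1 to 10.0%). The normal-approximation interval of 0 to 0% does not overlap it; the Wilson interval of 0 to 5.7% does.

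**The case against.** The strongest objection is that little depends on this interval. Tests, differences and their CIs come from the Firth model, the primary analysis is a separate MMRM, and a reader facing 0 of 45 would already have the model-based interval. This stands as a limit on importance. It does not repair the observed-rate interval printed beside it.

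Second, low rates are not shown to be likely. Take the sample-size assumptions (mean Week 12 reductions of 2.5 and 4.75 lesions, SD 3.6), treat the change as normal and assume a baseline count. The chance of at least a 50% reduction (placebo / active) is then 50% / 73% at a baseline of 5, 24% / 47% at 10, 8% / 22% at 15 and 2% / 7% at 20. These are upper bounds for HiSCR50, which also requires no increase in abscesses or draining fistulas. At a baseline of 5 to 10, Week 12 rates are therefore likely to sit where the normal approximation does little harm; at a true rate of 15%, two or fewer responders of 45 has a chance of only 2.7%. This also stands: the problem is chiefly one of early visits, or of patients with high baseline counts. The interval is nevertheless specified without regard to visit or count.

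Third, observed and model-based intervals estimate different things and would differ under Wilson too. That is true, but a zero-width interval beside one reaching about 10% is more than an ordinary difference.

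Fourth, the programming conventions in SAP section 8 suppress the percentage when a count is zero. They do not say whether the interval would still print, and they leave the negative limits at 1 and 2 of 45 untouched.

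**Conclusion.** The concern holds. The SAP names a method that gives wrong per-arm intervals at low counts. At n = 45, average coverage is about 82% instead of 90% for true rates of 2 to 10%, with a zero-width interval at 0 responders and negative lower limits at 1 and 2. Above about 15% the shortfall is small.

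The coverage figures are exact binomial results. Whether such low rates will occur is an assumption, as is the NRS30 denominator of 30. The redacted parts of the SAP could not be checked, although the method is stated without qualification in 5.4.5.

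The effect is confined to the descriptive intervals, and to Figures 14.2.2, 14.2.5 and 14.2.6 if they plot them. This is an optional improvement, not a threat to the trial's inference.

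**What to change.** In SAP 5.4.5, replace the normal approximation with the Wilson score 90% CI for each arm's observed responder rate. The exact interval is acceptable but conservative, so Wilson is the closer match to the nominal 90%.

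In SAP 5.4.6, state which 90% CI the responder figures show, and use the same Wilson or exact interval wherever the observed rate is plotted.

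The cost is about a sentence in each section and one programming option. Sample size, power, the Firth results and the p-values do not change.

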#### **5.4.6. Graphical Displays**

For change in inflammatory nodules and abscesses and change in HS-PGA, the LS Mean (90% CI) will be plotted over time. For the binary efficacy endpoints of proportion of patients achieving HiSCR50, NRS30, and [REDACTED] the responder rate (percentage) and 90% CI will be plotted over time by treatment group.

### **5.5. SAFETY**

All safety analyses will be performed on the Safety Population. Values for all safety variables will be listed by subject and visit (as applicable).

#### **5.5.1. Adverse Events**

Adverse events (AE) will be mapped to a PT and system organ classification (SOC) using MedDRA version 24.0.

An overall summary will be presented which includes the number of TEAEs and the number and percentage of patients who experienced at least one TEAE. This summary will also include:

- Any TEAE
- Any Serious TEAE
- Any Mild TEAEs
- Any Moderate TEAEs
- Any Severe TEAEs
- Any Related TEAEs (defined as Probably or Possibly Related)
- Any TEAEs leading to discontinuation of study drug
- Any Related TEAEs leading to discontinuation of study drug

- Commonly occurring TEAEs (defined as those AEs occurring in  $\geq 10\%$  of ATI-450 patients)

Adverse events of special interest (AESI) are captured on the AE eCRF page and include the following events: mouth ulceration, severe skin reaction which is considered to be related to the study drug, confirmed creatine kinase (CK)  $> 5X$  ULN without benign explanation, absolute neutrophil count  $< 1000$  cells/mm^3, and QTcF  $> 500$  msec or change from baseline QTcF  $> 60$  msec.

Additional summaries of TEAEs will be provided showing the number and percentage of patients who experienced at least one TEAE. These summaries will be presented by SOC and PT. If a participant reports the same PT multiple times within the same SOC, that PT will only be counted once within that SOC for that participant. As with the PT, if a participant reports multiple conditions within the same SOC, that SOC will only be counted once for that participant. In the summary, SOC will be listed in ascending alphabetical order; PTs will be listed in order of descending frequency for all participants within each SOC.

The occurrence of TEAEs related to study medication, TEAEs leading to discontinuation of study drug, study drug related TEAEs leading to discontinuation, AESIs, and serious adverse events (SAEs) will be tabulated by SOC and PT. An additional summary of TEAEs will be provided by SOC, PT and maximum severity. Most frequent TEAEs, defined as AEs occurring in 10% of ATI-450 patients, will be summarized by PT.

All AEs reported will be listed by individual subject, showing both verbatim and PT. All AEs reported with a start date prior to the initiation of study medication will be excluded from the TEAE tables but will be included in the listings.

Missing onset dates will be imputed as previously outlined in [Section 3.3.5](#) as required to determine TEAEs.

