### 1.1. **STUDY OVERVIEW**

This is a Phase 2a, randomized, double-blind, placebo-controlled study to investigate the efficacy, safety, tolerability, pharmacokinetics (PK), and pharmacodynamics (PD) of ATI-450 50 mg twice daily (BID) versus placebo in patients with moderate to severe HS.

The study will consist of an up to 28-day Screening Period, a 12-week treatment period, and a 30-day follow-up period. The total duration of the study for patients remaining until their final follow-up assessment will be up to 21 weeks. Patients will attend clinic visits on Days 1, 8, 15, 29, 43, 57, and 85 for safety, efficacy, PK, and PD assessments of the 12-week treatment period. A safety follow-up visit will be conducted 30 days after the last dose of study treatment for patients who completed the treatment period, as well as those who discontinue early.

Approximately 20 study centers in the United States are expected to participate in this study. Patients confirmed eligible at Baseline will be randomized in a 1:1 ratio to receive either ATI-450 tablets (50 mg BID) or matching placebo tablets BID. It is planned to randomize approximately 90 patients to obtain 45 patients per arm.

Study drug will be administered orally BID for 12 weeks. On clinic visit days, the morning dose of study treatment will be administered in the clinic.

The total duration of the study for patients remaining until their final follow-up assessment will be up to 21 weeks.

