## **5. STATISTICAL METHODS**

Descriptive statistical methods will be used to summarize the data from this study, with hypothesis testing performed for the primary and secondary efficacy endpoints. Unless stated otherwise, the term “descriptive statistics” refers to number of patients, mean, median, standard deviation, minimum, and maximum for continuous data, and frequencies and percentages for categorical data. For categorical variables, the denominator of percentages will be the number of patients with a

---

non-missing value at the visit and/or the scheduled time point. If a different denominator is used, this will be identified in the summary table.

All data collected during the study will be included in data listings. Unless otherwise noted, the data will be sorted first by treatment group, subject number, and then by date within each subject number. Assessments indicated as 'Not Done' will not be included in the listings.

The term 'treatment group' refers to all patients on the same dosing regimen. There will be two treatment groups in this study: Placebo BID and ATI-450 50mg BID.

All statistical testing will be one-sided and will be performed using a significance (alpha) level of 0.05 unless otherwise stated. P-values will be presented to three decimal places. For the efficacy endpoints, the ATI-450 treatment group will be tested versus Placebo via statistical inference.

The statistical analyses will be conducted with the SAS® software package version 9.4 or higher. All analyses will be subject to formal verification procedures. Specifically, results will be independently verified by a second programmer or statistician prior to issuance of the draft statistical report. All documents will be reviewed by the lead statistician to ensure accuracy and consistency.

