## **Section 14.3 Safety**

Table 14.3.1.1 Overall Summary of Adverse Events, Safety Population

Table 14.3.1.2 Treatment-Emergent Adverse Events by System Organ Classification, Preferred Term and Greatest Severity, Safety Population

Table 14.3.1.3 Treatment-Emergent Adverse Events by System Organ Classification and Preferred Term, Safety Population

Table 14.3.1.4 Treatment-Emergent Serious Adverse Events by SOC and PT, Safety Population

Table 14.3.1.5 Treatment-Emergent Adverse Events Related to Study Drug by SOC and PT, Safety Population

Table 14.3.1.6 Treatment-Emergent Adverse Events Leading to Discontinuation of Study Drug by SOC and PT, Safety Population

Table 14.3.1.7 Study Drug Related Treatment-Emergent Adverse Events Leading to Discontinuation of Study Drug by SOC and PT, Safety Population

Table 14.3.1.8 Adverse Events of Special Interest (AESI) by SOC and PT, Safety Population

Table 14.3.1.9 Summary of Most Frequent Treatment Emergent Adverse Events by Preferred Term, Safety Population

Table 14.3.4.1.1 Summary of Hematology and Coagulation Results and Change from Baseline by Analysis Visit, Safety Population

Table 14.3.4.1.2 Summary of Serum Chemistry Results and Change from Baseline by Analysis Visit, Safety Population

Table 14.3.4.1.3 Summary of Urinalysis Results and Change from Baseline by Analysis Visit, Safety Population

Table 14.3.4.2.1 Summary of Treatment-Emergent Abnormal Hematology and Coagulation by Analysis Visit Safety Population

Table 14.3.4.2.2 Summary of Treatment-Emergent Abnormal Serum Chemistry by Analysis Visit, Safety Population

Table 14.3.4.2.3 Summary of Treatment-Emergent Abnormal Urinalysis by Analysis Visit, Safety Population

Table 14.3.4.4 Summary of Laboratory Results by CTCAE Toxicity Grades for CK, Absolute Neutrophils, ALT, AST, and Bilirubin, Safety Population

---

Table 14.3.5.1 Summary of Vital Signs and Change from Baseline by Analysis Visit, Safety Population

Table 14.3.5.2.1 Summary of ECG Results and Change from Baseline by Analysis Visit, Safety Population

Table 14.3.5.2.2.1 Proportion of Patients with Abnormal Investigator ECG Interpretations by Analysis Visit, Safety Population

Table 14.3.5.2.2.2 Proportion of Patients with Abnormal Central ECG Interpretations by Analysis Visit, Safety Population

Table 14.3.5.2.3 Proportion of Patients with Noteworthy QT Changes by Analysis Visit, Safety Population

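### The common-TEAE line and Table 14.3.1.9 select terms by frequency in the ATI-450 arm alone, which in expectation tilts those two displays against ATI-450; an either-arm rule removes the tilt

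*SAP*

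**What the plan says.** SAP section 5.5.1 uses a frequency rule twice.

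- In the overall adverse event summary, the last of nine bullets is "Commonly occurring TEAEs (defined as those AEs occurring in" at least 10% of ATI-450 patients.
- Later in the section, for a separate table: "Most frequent TEAEs, defined as AEs occurring in 10% of ATI-450 patients, will be summarized by PT". The list of outputs names it: "Table 14.3.1.9 Summary of Most Frequent Treatment Emergent Adverse Events by Preferred Term, Safety Population".

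Neither rule refers to the placebo arm. The first carries an at-least sign; the second gives a bare 10%.

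The same section also plans TEAEs by system organ class and preferred term without a frequency cut-off (Table 14.3.1.3), a table by greatest severity (Table 14.3.1.2), tables of serious, related and special-interest events and events leading to discontinuation, and listings of all adverse events. Protocol section 9.4 has all data presented by treatment group. SAP section 5 confines hypothesis testing to the primary and secondary efficacy endpoints, so adverse events are described and not tested.

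**The concern.** A rule that looks at one arm treats the two arms differently. A term enters the display only if its observed ATI-450 count is high enough, so the displayed ATI-450 percentage is conditioned on being high while the placebo percentage beside it is not. The expected difference is then positive even with identical true rates. A term that reaches 10% on placebo but not on ATI-450 is left out of these displays.

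Safety is part of a secondary objective (SAP section 2), and a short table of common events is a natural source for a summary of the drug's profile against placebo. The term-level bias can be checked against Table 14.3.1.3. A pooled row counting patients with any common event cannot be rebuilt from that table, because one patient may have several terms.

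**Working it through.** **Inputs from the documents.** Arm size: "It is planned to randomize approximately 90 patients to obtain 45 patients per arm" (SAP section 1.1). Cut-off: 10% of 45 is 4.5, so a term is listed when 5 or more ATI-450 patients have it (5/45 = 11.1%).

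**Inputs assumed.** The documents give no adverse event rates. True term rates of 2% to 25%, equal in both arms unless stated, are assumptions shown as a range.

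**The plan's own figure.** No figure is given for the selection rule. The planned arm size can be checked through the stated power (SAP section 3.1; one-sided alpha 0.05). With difference 4.75 − 2.5 = 2.25, SD 3.6 and 45 per arm, the noncentrality is 2.25 / (3.6 × √(2/45)) = 2.965. With 88 degrees of freedom and critical value 1.662, the noncentral t gives 90.27%, which agrees with the stated 90.3%. Nothing below changes it.

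**Step 1: one term, no true difference.** Let X be the ATI-450 count, binomial with n = 45 and rate p.

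- Probability of listing: P(X ≥ 5).
- Mean ATI-450 rate once listed: E(X | X ≥ 5) / 45.
- Mean placebo rate: p, because placebo plays no part in the selection.

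For p = 10%: P(X ≥ 5) = 0.473, and the sum of x·P(X = x) over x ≥ 5 is 2.94. The listed mean is 2.94 / 0.473 / 45 = 13.8%, an excess of 3.8 points.

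| True rate, both arms | Probability listed | Mean ATI-450 rate if listed | Excess (points) |
|---|---|---|---|
| 4% | 0.03 | 11.9% | 7.9 |
| 8% | 0.29 | 13.0% | 5.0 |
| 10% | 0.47 | 13.8% | 3.8 |
| 15% | 0.83 | 16.6% | 1.6 |
| 20% | 0.96 | 20.5% | 0.5 |

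The largest excesses belong to terms that are seldom listed.

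**Step 2: omission from the two displays.** The chance that a term reaches 5 or more placebo patients but fewer than 5 ATI-450 patients is P(placebo ≥ 5) × P(ATI-450 < 5). With equal true rates of 5%, 10% and 15% it is 0.07, 0.25 and 0.14. With true rates of 5% on ATI-450 and 15% on placebo it is 0.825 × (1 − 0.073) = 0.77.

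**Step 3: the summary line, if it is one pooled row.** Patients with at least one selected term were simulated with independent terms and equal true rates in both arms, averaging over trials in which at least one term was selected (4,000 trials for the first row, 8,000 for the others).

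| Assumed true term rates | ATI-450-only rule, ATI-450 vs placebo | Gap (points) | Either-arm rule |
|---|---|---|---|
| 36 terms: 6 at 8%, 10 at 5%, 20 at 2% | 29.6% vs 17.5% | 12.1 | 35.5% vs 35.4% |
| 30 terms: 3 at 8%, 7 at 5%, 20 at 2% | 20.7% vs 11.5% | 9.2 | 22.4% vs 22.4% |
| 40 terms: 15, 12, 10, 8, 8, 6, 6, 5, 5, 5%, then 10 at 3%, 20 at 2% | 37.6% vs 28.6% | 9.0 | 43.2% vs 43.2% |
| 14 terms: 3 at 20%, 1 at 15%, 10 at 3% | 55.9% vs 54.0% | 1.9 | 57.0% vs 57.1% |

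In the first two rows every true rate is below 10%, so every selected term crossed by chance. In the last, truly common terms dominate and little bias is left. Counting trials with no selected term as zero gives 27.8% vs 16.4% in the first scenario, a gap of 11.4 points.

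**The case against.** The strongest reply is that this is a small matter of presentation with a legitimate purpose: a sponsor may want to show which events are common on its own drug. Much of that stands.

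- A reader might infer that events commoner on placebo are hidden from the report. The documents do not support this. Table 14.3.1.3 has no cut-off, orders terms within each class by frequency over all participants, and every event is listed. Such terms are missing only from Table 14.3.1.9 and one summary line.
- A reader might infer that the overall summary as a whole overstates ATI-450 risk. Only one of its nine bullets uses arm-based selection.
- A reader might infer that the rule could mask harm. It runs the other way, and no adverse event test rests on it.
- The pooled row is an interpretation. The other eight bullets begin with the word Any and this one does not; the SAP does not say whether it is one row or one row per term. The figures in Step 3 depend on the first reading.
- The difference between a bare 10% and at least 10% has no analytic effect at 45 per arm, since 4.5 patients cannot occur. Aligning the two is editorial.
- An either-arm rule removes the direction of the bias but not chance crossings: listed terms with true rates of 4% to 10% would still show an average absolute gap of about 6 to 8 points, now equally likely in either direction.

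What the reply does not answer is the asymmetry. In the two displays concerned, the expected gap under no effect is positive for ATI-450, and a symmetric rule at almost no cost brings it to zero.

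**Conclusion.** The concern holds for two displays: the common-events line of the overall summary and Table 14.3.1.9. Selection on the ATI-450 arm alone inflates that arm's side of both in expectation, and omits from both the terms that are common only on placebo. For a listed term the average excess falls from 7.9 points at a true rate of 4% to 0.5 points at 20%, while the probability of listing rises from 0.03 to 0.96. For a pooled summary row the excess is about 2 to 12 points, smaller when truly common terms dominate, and about 0 under an either-arm rule.

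These sizes rest on 45 patients per arm, equal true rates in the two arms and, for the pooled row, on the assumed number and rates of terms, independence between terms and the pooled-row reading. The direction does not depend on the particular rates. This is a minor point: it affects descriptive displays only, and no efficacy result or test changes.

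**What to change.** In both places in SAP section 5.5.1, define common TEAEs as preferred terms occurring in at least 10% of patients in either treatment group, and show both arms for every selected term. Using the same words twice also settles the threshold wording. In the same edit, state whether the summary line is one row counting patients with any such term or one row per term.

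The cost is a few words in the SAP and a few more table rows. In the 40-term scenario the average number of selected terms rises from 3.1 to 4.8, and in the 30-term scenario from 1.4 to 2.6. No data collection, sample size or test is affected.
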